## 1.0 PROTOCOL SUMMARY AND/OR SCHEMA

Purpose:	The objective of this study is to evaluate hepatic arterial embolization for hepatocellular cancer using microscopic beads and the same microscopic beads loaded with doxorubicin.
Study design:	Single center, single blind, prospective, randomized phase II controlled, to be conducted without crossover with patients recruited over a 2 year period
Study agents:	Biocompatibles LC Bead ( Beads + doxorubicin ), 100-300 microns, 150 mg doxorubicin per procedure with additional 100-300 micron and larger size beads (Bead Block) as necessary to achieve stasis  Bead Block ( Beads ) microsphere, 100-300 micron with additional larger size beads as necessary to achieve stasis
Limitations of Study	LC Bead and Bead Block are both tinted blue. Because doxorubicin is red, the addition of doxorubicin to the embolization microspheres will change the color of the spheres to some degree, and thus it may be possible for the interventional radiologist performing the embolization to differentiate between the two embolics. All other participants performing image and data analysis will be blinded.
Enrollment:	100 patients will be enrolled, 50 in each study arm
Clinical site:	Memorial Sloan-Kettering Cancer Center, NY, NY
Primary endpoint:	Response to treatment by RECIST criteria
Secondary endpoints:	

• Tumor necrosis

• Toxicity

• Time to progression

• Survival

Safety endpoint:	The safety endpoint will be treatment related Serious Adverse Event (SAE) rate, defined by SAE occurring within 30 days of a procedure. SAE is defined as a grade 3 or 4 adverse event using the Common Terminology Criteria for Adverse Events (CTCAE) 3.0.
Primary analysis:	Intent-to-treat analysis
Secondary Analysis:	Per protocol analysis and treated population analysis
Principle Investigator:	[name]

Member  
Department of Radiology  
Memorial Sloan-Kettering Cancer Center  
[name]  
[name]

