### 17.2 Serious Adverse Event (SAE) Reporting

An SAE is defined as a grade 3 or 4 adverse event using the Common Terminology Criteria for Adverse Events (CTCAE) 3.0. For the purpose of this study, an unanticipated device effect (UADE) will mean any event that is rarely observed after hepatic arterial embolization, rarely seen in patients hospitalized with diagnosis of cancer or patients receiving doxorubicin.

Any SAE must be reported to the IRB/PB as soon as possible but no later than 5 calendar days. The IRB/PB requires a Clinical Research Database (CRDB) SAE report be submitted electronically to the SAE Office at [[contact]](mailto:[contact]) containing the following information:

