#### Data Needing to be Entered:

- The date the adverse event occurred
- The adverse event
- Relationship of the adverse event to the treatment (drug, device, or intervention)
- If the AE was expected
- The severity of the AE
- The intervention
- Detailed text that includes the following information:
  - A explanation of how the AE was handled
  - A description of the subject's condition

- Indication if the subject remains on the study
- If an amendment will need to be made to the protocol and/or consent form

The PI's signature and the date it was signed are required on the completed report.

For IND/IDE protocols:

Only UADEs and patient deaths will be reported to the FDA as they occur. For these reports, The CRDB AE report should be completed as above and the FDA assigned IND/IDE number written at the top of the report. If appropriate, the report will be forwarded to the FDA by the SAE staff through the IND Office. **All other SAEs will be recorded as part of the study's data and will be included in the study's progress reports to the FDA.**

This study will collect all SAEs that occur from date of consent until the patient is off study. Since elevation in liver function tests is expected in the immediate post treatment period, no elevation in liver function tests occurring within 2 weeks following treatment will be reported as an SAE, although all elevations will be recorded and captured among the data for the study. The following is a list of the liver function tests: Alkaline Phosphatase, ALT, AST, and Bilirubin. All other elevations to Grade 3 or 4, along with any hospitalization will be reported as SAEs and only reported to the FDA as they occur if considered an UADE.

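### The 30-day SAE rate, read literally, omits fatal events, and SAE collection can stop before day 30

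*Combined protocol and SAP*

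**What the plan says.** Section 1.0 of the combined protocol and SAP makes the safety endpoint the "treatment related Serious Adverse Event (SAE) rate, defined by SAE occurring within 30 days of a procedure". The next sentence gives the severity rule: "SAE is defined as a grade 3 or 4 adverse event using the Common Terminology Criteria for Adverse Events (CTCAE) 3.0". Section 17.2 gives the same rule: "An SAE is defined as a grade 3 or 4 adverse event". Neither place mentions fatal events.

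Later in Section 17.2, under the instructions for IND/IDE protocols, the text says "Only UADEs and patient deaths will be reported to the FDA as they occur" and shortly afterwards "All other SAEs will be recorded as part of the" study data. The section also widens and narrows what is reported. It says "All other elevations to Grade 3 or 4, along with any hospitalization will be reported as SAEs", and it says "no elevation in liver function tests occurring within 2 weeks following treatment will be reported as an SAE", while still recording those early elevations as data.

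On the collection period, Section 17.2 says "This study will collect all SAEs that occur from date of consent until the patient is off study". Section 13.0 lists the reasons for removal:

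- less than 5% necrosis after the initial treatment;
- a large increase in tumor measurements after later treatments;
- unacceptable toxicity at any time;
- pregnancy;
- ineligibility discovered at any time;
- non-compliance;
- patient preference.

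Section 10.0 places the first response CT 2-3 weeks after completed treatment. Section 14.0 does not mention the SAE rate.

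**The concern.** Two separate features could make the reported rate too low.

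The first is the definition. An endpoint limited to grades 3 and 4 counts severe and life-threatening events but, on its literal wording, not the worst outcome. Section 11.0 foresees death as a very rare complication of embolization, so the case is not purely theoretical. Two analysts working from this text could count the same death differently.

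The second is the window. The endpoint needs 30 days of observation after each procedure, but collection is tied to study status. A patient who leaves early is then treated as event-free for days on which nobody was asked to look. Several of the removal reasons (toxicity, poor response, preference) are unlikely to be unrelated to how the patient is doing, and they could differ between arms.

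The trial is meant to inform whether the added side effects of doxorubicin merit further study, and this is the endpoint labelled as safety.

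**Working it through.** The documents give no SAE rate, precision or power figure for this endpoint, so there is no stated number to reproduce. The check is a comparison of text, day counts, and an illustration of scale.

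**Step 1: does a death count?**

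| Place | What it supports |
|---|---|
| Section 1.0, safety endpoint | Grade 3 or 4; fatal events not named |
| Section 17.2, opening definition | Same rule; fatal events not named |
| Section 17.2, FDA routing | Deaths named, then the other SAEs, which suggests that deaths are SAEs |

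The two definitions agree with each other. The third place points the other way only by implication. On the literal definition, a patient who dies within 30 days with no separately recorded grade 3 or 4 event is not counted.

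**Step 2: how much of the window can be lost?**

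Inputs: a 30-day window (Section 1.0), collection ending at off study (Section 17.2), and the response CT at days 14-21 (Section 10.0). For removal on day d after the last procedure:

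days uncollected = max(0, 30 - d)

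- d = 14: 30 - 14 = 16 days, or 16/30 = 53% of the window
- d = 21: 30 - 21 = 9 days, or 9/30 = 30% of the window
- d = 30 or later: 0 days

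For the low-necrosis route these are upper bounds. They assume removal on the day of the CT. Section 12.0 sends the scan to an independent laboratory for volumetry, and no turnaround or removal date is given. Removal for toxicity, ineligibility, pregnancy, non-compliance or preference is not tied to the CT, so the same formula applies on whatever day it occurs.

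**Step 3: which early leavers matter?**

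If the rate is per patient, a patient removed because of a grade 3 or 4 toxicity is already counted, and nothing is lost. The rate changes only when a patient with no counted SAE leaves before day 30 and then has a qualifying event before day 30.

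**Step 4: scale.**

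The documents do not say whether the rate is per patient or per procedure. Taking it as per patient (assumption), with 50 patients per arm:

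- One omitted patient: 1/50 = 2.0 percentage points.
- With 10 of 50 patients counted (an assumed count), the rate is 20% (exact 95% CI 10.0% to 33.7%). One more gives 11/50 = 22% (11.5% to 36.0%).
- Half-width at an assumed 20% rate: 1.96 × sqrt(0.2 × 0.8 / 50) = 11.1 points. At an assumed 40%: 1.96 × sqrt(0.4 × 0.6 / 50) = 13.6 points.

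One omitted patient is therefore well inside sampling error. The number of omissions cannot be derived from the documents and may be zero.

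**The case against.** The strongest reply is that little is hidden. Survival is a secondary endpoint, a death on treatment ends time to treatment failure, and Section 17.2 sends deaths to the FDA. Toxicity graded by CTCAE 3.0, with no restriction to grades 3 and 4, is a separate secondary endpoint. No test or stopping boundary uses the SAE rate, and the primary endpoint is untouched. All of this stands, and it limits the size of the point. It does not settle whether a death belongs in the SAE rate, and it does not restore a non-fatal SAE that occurs after removal.

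Three stronger readings are tempting, and the documents do not support them.

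- A reader might infer that Sections 1.0 and 17.2 contradict each other about deaths. The two definitions match. The contrary hint lies in a paragraph about routing reports to the FDA, where the wording may simply mean SAEs not already sent. The accurate description is that the inclusion of deaths is suggested but not stated.
- A reader might build a chain in which a bilirubin rise between two staged sessions makes the patient ineligible, is exempt as an SAE, and closes collection. Section 6.0 applies eligibility before each treatment, but Section 9.0 counts the two sessions as a single treatment. Section 6.1 ties the laboratory values to registration. Section 17.2 exempts early elevations from SAE reporting but still records them, and it does not say that they leave the endpoint.
- A reader might conclude that the plan conceals deaths. The other endpoints and the FDA reporting rule show otherwise.

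**Conclusion.** The point holds in two limited parts. As written, the safety endpoint does not count a fatal event that has no accompanying grade 3 or 4 record, and SAE collection may end inside the endpoint's own 30-day window. Both can only lower the reported rate.

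The likely effect is small: 2 points per omitted patient in an arm of 50, assuming a per-patient rate, with an unknown and possibly zero number of omissions. The loss of 9 to 16 days applies to removal on the day of the 2-3 week CT and is a ceiling for that route. The correction is worth making because it is specific and inexpensive, and because it removes a discretionary choice from the endpoint labelled as safety. It is no threat to the response-rate estimates.

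**What to change.** In Sections 1.0 and 17.2, define the endpoint SAE as a CTCAE 3.0 event of grade 3 or higher, including fatal events. In Section 17.2, collect SAEs from consent until the later of the off-study date or 30 days after the last embolization. The removal criteria in Section 13.0 need not change.

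The cost is a wording amendment and a day-30 SAE check for the few patients who leave early. The reported SAE rate may come out slightly higher.

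Optional in the same amendment: state whether the rate is per patient or per procedure, say whether hospitalizations and early liver-test elevations count in the endpoint or only affect reporting, and tabulate 30-day mortality by arm beside the SAE rate.

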### Protocol Schema

TPCT = Pre-treatment triple-phase CT

TPCT = CT to be used to determine response to treatment (first study endpoint)

TPCT - If there is evidence of persistent or progressive tumor on this follow-up CT (but not meeting criteria for treatment failure), patients are re-treated within their treatment arm, and then re-enter F/U pathway. Treatment failure = < 5% necrosis following the initial treatment, or development of >50% increase in uni-dimensional measurement (RECIST) following subsequent treatments.

## 2.0 OBJECTIVES AND SCIENTIFIC AIMS

### **Primary Objective**

In this study one group of patients with hepatocellular cancer (HCC) will undergo hepatic arterial embolization using microscopic beads + doxorubicin and another group with the microscopic beads alone. Response to treatment will be determined in each group by conventional RECIST criteria. Since there is no historical data on imaging response to treatment for either group, the

study will be randomized. The primary objective will be to estimate the response rate in the two arms.

### **Secondary Objectives**

1. Quantify the amount of tumor necrosis before and after initial treatment in both groups by CT volumetry, and correlate with response to treatment by RECIST criteria.
2. Evaluate toxicity, time to progression (TTP) and survival in each treatment arm.  
Determine if initial imaging response to treatment, as manifested by either RECIST criteria or volume of necrosis correlates with either TTP (by RECIST or volumetric method) or survival.

## **3.0 BACKGROUND AND RATIONALE**

### **Background:**

#### **Hepatocellular Carcinoma**

Over 1 million new cases of hepatocellular cancer are diagnosed in the world each year. Primary liver cancer is not common in the United States; however the incidence is rising primarily because of the spread of hepatitis C. There are over 15,000 deaths in the U.S. each year from primary cancers of the liver and biliary tree. Hepatocellular carcinoma is one of the few cancers with well-defined major risk factors [Bosch et al 1999, Colombo 2003]. It develops within cirrhotic livers in 80% of cases and this pre-neoplastic condition is the strongest predisposing factor [Colombo 2003]. The cirrhosis is most often associated with either hepatitis B or C, or excessive alcohol use. Patients with hepatitis B or C who also consume alcohol increase their risk of developing HCC [NCI web site]. Because there was no test for hepatitis C before 1992, many Americans acquired the hepatitis C virus through blood transfusions received before that time. As awareness of hepatitis C virus transmission becomes more widespread, there is increased screening for hepatitis C, and a concomitant increase in the number of patients diagnosed with hepatocellular cancer. Currently 10-15,000 new cases of HCC are diagnosed in the US each year and it is estimated this number may double given the spread of hepatitis C [Wong JB 2000].

#### **Surgical/Medical Therapy**

Hepatocellular cancer is potentially curable by surgical resection, but most patients are not resectable at the time of presentation either because of the extent of the tumor or the severity of their underlying liver disease. Over 60% of patients who are resected will develop disease elsewhere in the liver within 5 years of resection as a result of their underlying liver disease [Sugioka A, 1993, Cha C, 2003]. Systemic chemotherapy has never been shown to be effective. The ubiquitous nature of this disease, and the lack of effective traditional therapies, have led investigators to attempt many novel methods of treatments, including percutaneous ablation with alcohol, radiofrequency ablation, cryoablation and various methods of arterial infusion and embolotherapy. Hepatic arterial chemoembolization has become the accepted standard of care for patients who are not surgical candidates although, to date, no study has demonstrated a survival advantage to chemoembolization compared to particle embolization without chemotherapy [Brown DB, 2006].

## **Local/Regional Therapy**

Studies performed in the early 1950s established that the primary blood supply to liver tumors was from the hepatic artery [Breedis C, 1954]. Before the development of sophisticated methods for liver resection, hepatic ligation was sometimes performed in unresectable cases, however it was not found to be effective owing to the large number of collateral routes to the hepatic circulation, as demonstrated by Michels in 1953 [Michels NA, 1953]. These collateral pathways result in rapid reperfusion of the hepatic vasculature distal to the ligature, not unlike that which is seen following proximal arterial embolization. Parallel with the development of angiography, catheter directed techniques of treating liver tumors began to be explored in the late 1970s and early 1980s. These therapies were particularly desirable for treating patients with hepatocellular cancer (HCC), for which there was no effective non-surgical treatment, and very few patients who were candidates for resection. Hepatic arterial embolization capitalizes on the dual blood supply to the liver. 75 to 80% of the trophic blood supply to the normal liver parenchyma arises from the portal vein, whereas the primary vascular supply to hepatocellular cancer, and most liver metastases, is from the hepatic artery. This dual blood supply, coupled with the relative ease of catheterizing the hepatic artery, allowed for the delivery of various agents intra-arterially that are intended to kill the tumor cells while having little or no effect on the normal hepatic parenchyma, and ideally no systemic effect.

## **Supporting Preliminary Data**

Despite the fact that no systemic chemotherapy had ever been shown to be effective against hepatocellular cancer, chemotherapy has been administered by arterial infusion in an effort to deliver a higher concentration of chemotherapy directly to the tumor in the hope of enhancing the effect of the drug while limiting the systemic effect. It had been noticed that lipiodol, when administered intra-arterially, was taken up by most hepatic malignancies, and particularly HCC. Initially it was thought that intra-arterial lipiodol alone might have a therapeutic effect on HCC. This was soon discredited [Takayasu K, 1987], however the idea of using lipiodol as a carrier came into vogue. Pharmacokinetic studies failed to demonstrate high concentrations or prolonged retention of chemotherapeutic agents in liver tumors, or any difference in clinical outcome when these agents were administered alone, or with lipiodol [Carr BI, 1993, Johnson PJ, 1991, Madden MV, 1993]. A pharmacokinetic advantage to the use of chemotherapy and lipiodol could only be convincingly shown when unconventional methods were used to dissolve the chemotherapeutic agents in lipiodol [Konno T, 1990], or a lipophilic chemotherapeutic agent was mixed with the lipiodol [Egawa H, 1990], methods that are not used in clinical practice in the United States.

Based on data available in the literature in the early 1990s, it seemed as if the primary benefit from transarterial chemoembolization (TACE) for HCC might in fact be derived from ischemia related tumor necrosis, and not the chemotherapeutic agents or the lipiodol [Nakao N, 1991, Ngan H 1996]. Eliminating the chemotherapeutic agents would eliminate chemotherapy related side effects associated with TACE, decrease the cost of treatment, and reduce the technical difficulties of working with chemotherapy. Intra-arterial chemotherapy is conventionally dosed based on body surface area and not based on tumor volume or vascularity. A fixed amount of chemotherapeutic agent or agents are mixed with a fixed amount of lipiodol, and emulsified. This emulsion is then administered intra-arterially to the target area of the liver. Delivering an intra-arterial emulsion of chemotherapy is not straightforward. In some cases it is impossible to deliver the entire dose to smaller or less vascular tumors. In the case of large vascular tumors the entire dose of chemotherapy and lipiodol might be used early in the procedure while rapid flow

to the tumor persists. The dose of chemotherapeutic agent is not proportional to tumor volume. At many centers TACE is performed non-selectively, exposing the uninvolved liver to the chemotherapy/lipiodol/particle cocktail. This may adversely affect the “normal” liver and result in deterioration of liver function.

To date, no study has demonstrated a difference in survival between patients treated with “bland” embolization (TAE) and those treated with chemoembolization (TACE). A metaanalysis of randomized controlled trials between 1980 and 2000 included 2466 patients, 178 of whom received “non-active” treatment [Camma C, 2002]. This study concluded that TACE significantly reduces overall 2 year mortality, but that TACE was not more effective than TAE. The most recent, and frequently cited, randomized controlled study comparing TACE, TAE, and supportive care [Llovet JM, 2002] again demonstrated a survival advantage to TACE over supportive care, but was stopped before any statement could be made about the utility of TAE. Despite this, chemoembolization with lipiodol has become accepted worldwide as an important treatment option for patients with unresectable HCC.

[figure not shown]
### **Preliminary Data**

For the past 14 years the protocol used for hepatic arterial embolization at MSKCC employs only an embolic particle targeted to cause terminal vessel blockade and, as a result, ischemic tumor cell death. Knowing that occlusion of the more proximal hepatic vessels results in the development of intrahepatic collateral flow and continued perfusion of the more distal vascular bed, the smallest particles available are used to cause blockade of the terminal hepatic vasculature in an effort to enhance ischemia. Initially, polyvinyl alcohol (PVA) particles were in widespread use and the smallest particles available were 100  $\mu$ , later 50  $\mu$  particles became available. We published our early results using these particles to treat 46 patients in 1998 [Brown KT, 1998]; obtaining results that were not substantially different than those reported contemporaneously by others using various methods of chemoembolization. Since then we have begun using spherical embolic particles, hydrophilic, nonresorbable microspheres produced from an acrylic polymer. Using these particles, and treating over 300 patients with similar characteristics to those reported on by Lo [Lo CM, 2002] and Llovet [Llovet JM, 2002] we have achieved 1, 2, and 3 year survival of 85%, 68%, and 42% [Maluccio 2006]. These results are better than those reported by Lo (56%, 31%, and 26% at 1, 2, and 3 years), and similar to the 82% 1 year and 63% 2 year survival reported by Llovet, but in a much larger group of patients.

A microscopic bead has been developed that can be used as an embolic agent alone, or loaded with doxorubicin to deliver high concentration of the drug to a target tumor within the liver while limiting systemic exposure. Before this agent that is much more expensive than conventional embolic material comes into widespread use, it would be valuable to assess its effectiveness. Since the agent is itself an embolic and can be used without loading doxorubicin, the opportunity exists to determine to what extent the addition of chemotherapy enhances the effect of embolization alone. Although survival is clearly the most important endpoint in evaluating treatments for HCC, survival studies require several years of follow-up in these patients, whereas preliminary data regarding response to treatment can be obtained using imaging. Traditionally, Response Evaluation Criteria In Solid Tumors (RECIST) have been used to evaluate response to treatment, and will be used as a primary endpoint in this study. These criteria are based on the product of bi-dimensional orthogonal measurements of a treated lesion, and do not take into account the degree of tumor necrosis resulting from treatment. The Barcelona-2000 EASL conference [Bruix J, et al 2001] concluded that tumor necrosis is an important indicator of

response to treatment for HCC, and recommended that changes in viable tumor area, rather than overall tumor area, be used to assess response. RECIST criteria have been found to be insensitive when used to evaluate other tumors that develop significant necrosis in response to treatment, such as the response of GIST tumors to Imatinib [Benjamin RS, et al 2006]. In this study, % tumor necrosis will serve as a secondary endpoint. Tumor necrosis will be quantified on contrast enhanced CT scans using an automated volumetric method, and the relationship of tumor necrosis to response as measured by RECIST criteria will be determined. These 2 measures of response to treatment will be correlated with TTP and survival in an attempt to establish the utility of one or the other as a surrogate outcome marker.

Bead Block is a compressible hydrogel polyvinyl alcohol (PVA) microsphere available in sizes ranging from 100  $\mu$ m to 900  $\mu$ m. Manufactured by the same company, LC Bead is the same microsphere available in the same sizes. This agent is called DC Bead in Europe and Asia. It is intended to be loaded with doxorubicin in order to deliver a local, sustained release dose of doxorubicin to a tumor when used intra-arterially. A pharmacokinetic study [Geschwind 2004] has demonstrated sustained drug concentration within VX-2 tumor implanted in the liver of New Zealand white rabbits at 14 days, with low plasma concentration of doxorubicin at all times. The peak concentration of doxorubicin in the tumor is observed at 72 hours following treatment - demonstrating that these drug eluting beads do result in slow, local, sustained delivery of doxorubicin to the liver tumor. The amount of doxorubicin in the tumor is approximately 100 times greater when delivered from the drug eluting bead compared to direct intra-arterial injection. In addition, there is an 80% reduction in systemic availability of doxorubicin when using drug eluting bead. At 14 days there was also a significant increase in the fraction of non-viable tumor cells in animals treated with the drug eluting bead. Phase I/II clinical trials have been conducted in Asia and Europe using these doxorubicin eluting beads with the first cohort in each trial for dose escalation, and the second for efficacy [Attachment, DC Bead Product monograph]. A maximum dose of 150 mg of doxorubicin was given in a single procedure, and there was no dose limiting toxicity in either of the trials. In the Barcelona dose escalation trial, the peak level of doxorubicin was 2 log orders lower than that seen with TACE or intraarterial doxorubicin (Figure 1). The peak plasma concentration was reached immediately (5 minutes) in each group, averaged  $79 \pm 38$  ng/ml, with no significant differences between the groups, and serum level of doxorubicin was undetectable by 7 days. The AUC of the patients receiving the doxorubicin eluting bead was also significantly lower than patients treated with TACE or intra-arterial doxorubicin. The second cohort received 150 mg of doxorubicin per treatment with no systemic effects of doxorubicin. There was an objective response of 78% by EASL criteria at 6 months, with 30% CR.

**Figure 1** Combined plasma doxorubicin concentration-time curves according to dose groups (mg of doxorubicin)

Although trans-arterial chemoembolization (TACE) has become the standard treatment for patients with unresectable HCC, there has never been convincing evidence that the chemotherapy used for TACE remains in prolonged contact with the tumor in high concentration, or that there is any difference in survival when chemotherapy is added to the embolization agents. With the recent availability of drug eluting beads that have been shown to result in high local concentrations of chemotherapy (LC Bead) when used for embolization of HCC, it is possible to perform a study that evaluates the specific role of a chemotherapeutic agent (doxorubicin) delivered intra-arterially for the treatment of HCC. The results of this study are intended primarily to estimate response to treatment within the study and control groups. They may also help to clarify the role of chemotherapy when added to the ischemic effect of arterial embolization. A substantial difference in response to treatment would serve as a signal that the doxorubicin eluting bead may improve outcome in patients with HCC, and warrants further study. Coupled with an increase in TTP or survival, this might serve as the basis for an appropriately powered phase III trial. In addition, this study may validate a new imaging technique for evaluating response to treatment, and indicate if this imaging response to treatment may be used as a surrogate biomarker for outcome.

The expected outcomes of this study are to determine the response to treatment following arterial embolization of HCC using microspheres alone or microspheres + doxorubicin by RECIST criteria, and to determine the % tumor necrosis that results following treatment in each group. The response to treatment by RECIST criteria will be correlated with % tumor necrosis in both groups, and the relationship of both of these response parameters to TTP and survival will be assessed. The study may serve to validate an automated volumetric method of assessing response to treatment, and determine if this imaging response to treatment can be used as a surrogate biomarker for outcome. The findings will increase our understanding of how regional hepatic arterial therapies work, and may improve upon current imaging methods of assessing response to treatment. This study will offer a preliminary assessment of whether the additional expense, complexity, and potential side effects of adding chemotherapy to arterial embolization are worthy of further investigation. The results of this study are important not only for patients with HCC, but also for patients with other hypervascular liver tumors that are commonly treated with hepatic embolization.

